Objective 2 is a pragmatic cluster randomized trial. We have partnered with two rural healthcare systems (one in eastern Kentucky and one in Western Kentucky) for this study. Two clinics from each system will be randomized to participate in the intervention (4 total intervention sites) and the remaining clinics will serve as the control sites. The intervention consists of health information technology (including an automated patient identification system and bidirectional e-referral system connecting clinics to the DSMES providers) and a practice facilitation collaborative. The collaborative is a structured, facilitated process that brings together teams from different organizations to learn from one another. The collaborative utilizes the Model for Improvement, a quality improvement approach designed by the Institute for Healthcare Improvement that uses rapid cycle quality improvement – repeated PDSA (plan do study act) cycles meant to identify care quality barriers and rapidly implement and measure change. Teams from intervention clinics will apply this quality improvement strategy to identify and address quality gaps in diabetes care and DSMES utilization at their clinics. Practice facilitators on the study team will provide individualized coaching (practice facilitation) to clinics in the intervention arm of the study. We will assess the effect of the interventions on DSMES referrals (primary outcome), by comparing rates of referrals between intervention and control clinics (clinics within the healthcare system not randomized to the intervention). Secondary outcomes include DSMES attendance, patient satisfaction and diabetes knowledge, A1c control, and intervention feasibility and acceptability.

Objective 3 involves surveys and interviews with clinic staff that participated in the intervention and DSMES providers from the geographic areas where the intervention took place. Interviews will be conducted via phone and audio will be recorded. The goal of Objective 3 is to understand how the various implementation strategies embedded within the practice facilitation collaborative and clinical context influenced DSMES uptake to inform future refinement for program replication and scale-up.

Attachments

Subject Recruitment Methods & Advertising

Describe how the study team will identify and recruit subjects. Please consider the following items and provide additional information as needed so that the IRB can follow each step of the recruitment process.

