Objective 2: Baseline measures include patient demographics (sex, race/ethnicity, insurance coverage, rural/urban distribution), A1c control (mean A1c, % of patients with A1c >9%) and blood pressure. Clinics will also report number of DSMES referrals and DSMES attendance from the 9-month baseline period. In addition to baseline data, control and intervention clinics will generate monthly reports from their electronic health record system to track DSMES referrals and A1c control. DSMES attendance will also be reported by the clinics based on feedback data from the bidirectional referral system linking clinics with DSMES providers. All data will be examined at the clinic level and will be de-identified/aggregated to the clinic level prior to being shared with our study team. The following data is being extracted from patient electronic health records by clinic staff: DSMES referrals (% referred/% eligible at the clinic level), DSMES attendance (% attended/% referred at the clinic level), A1c Data (mean A1c levels and % with A1c >9% at the following time points will be extracted from electronic health record data and de-identified/aggregated into intervention vs control clinics as well as for the subset of patients within intervention vs control clinics that attended DSMES: baseline, monthly during the intervention and for the 6 months following intervention. In addition to the data being extracted from patients' electronic health records, we will also be receiving data from the DSMES providers on patient satisfaction with the class and diabetes knowledge. This outcome will be reported to the study team monthly for all patients from study clinics who attended DSMES classes during the 9-month study + 6 month follow-up period. Patient satisfaction and diabetes knowledge will be evaluated using de-identified data from patient surveys that are routinely collected by DSMES providers for all individuals immediately following DSMES attendance. KDPH will provide the study team with de-identified data for all patients from the two participating healthcare systems who attend DSMES (aggregated to the clinic level). All data used in Objective 2 is data that is routinely collected; no additional data will be collected as a part of the study.

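### Diabetes knowledge and patient satisfaction are observed only in patients who attended DSMES, so a between-arm difference in either is not an unbiased effect of the randomised intervention; label both as descriptive.

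*Combined protocol and SAP*

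**What the plan says.** The Study Design section states that "Objective 2 is a pragmatic cluster randomized trial". The assigned intervention is health information technology plus a practice facilitation collaborative. The DSMES class is delivered by the DSMES providers and is not listed as a component of what is randomised.

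Right after the sentence on assessing the intervention's effect on referrals by comparing intervention with control clinics, the same section says: "Secondary outcomes include DSMES attendance, patient satisfaction and diabetes knowledge, A1c control, and intervention feasibility and acceptability". The Objective 2 text under Records, Privacy, and Confidentiality repeats this list in the same position.

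Research Procedures (Objective 2) gives the data source: "we will also be receiving data from the DSMES providers on patient satisfaction with the class and diabetes knowledge". These are "reported to the study team monthly for all patients from study clinics who attended DSMES classes during the 9-month study + 6 month follow-up period", and they are taken from "patient surveys that are routinely collected by DSMES providers for all individuals immediately following DSMES attendance". Attenders from both healthcare systems are covered, so both arms are included, and the data reach the study team as clinic-level aggregates. The baseline list ("Baseline measures include patient demographics (sex, race/ethnicity, insurance coverage, rural/urban distribution), A1c control", then blood pressure and clinic counts of referrals and attendance) contains neither measure. The section closes: "All data used in Objective 2 is data that is routinely collected; no additional data will be collected as a part of the study".

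**The concern.** A randomised comparison is protected only if the patients compared were defined before, or independently of, the assigned intervention. Here the measured group is formed by attendance. The Objectives section hypothesises that the intervention will increase DSMES use, and attendance is itself a secondary outcome. The intervention therefore helps decide who has a knowledge or satisfaction score.

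Two wrong conclusions become possible if the arms are compared on these scores:

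- **False null.** If the class teaches equally well in both arms and the attenders are alike, the expected difference is zero however many more patients the intervention brings to class.
- **Selection artefact.** If the additional attenders differ from those who would have come anyway, the means differ although nobody's knowledge or satisfaction was changed by the assignment.

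The Data and Safety Monitoring section says the pilot is meant to indicate the approximate size of effectiveness, and the Objectives section says it will supply preliminary data for a larger grant application. Either error could carry forward into that next design.

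**Working it through.** The plan states no effect size, standard deviation, sample size or analysis for these two outcomes, so there is no figure to reproduce. The check is first structural, then illustrative.

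**Structure, from Research Procedures (Objective 2)**

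| Outcome | Who has a value | When |
|---|---|---|
| A1c | All clinic patients by arm, and the attender subset | Baseline, monthly during the intervention, and the 6 months after it |
| Knowledge, satisfaction | Attenders only | Immediately after the class |

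A1c has a population that does not depend on attendance. Knowledge and satisfaction do not.

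**Illustration 1: mean scores (all inputs assumed).** Per 1,000 eligible patients in each arm, 50 control patients (5%) and 150 intervention patients (15%) attend. Control attenders score 80%, as do the first 50 intervention attenders. The other 100 score *x*. The intervention mean is (50 × 80 + 100 × *x*) / 150.

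| *x* | Intervention mean | Difference from control |
|---|---|---|
| 85% | 12,500 / 150 = 83.3% | +3.3 points |
| 80% | 12,000 / 150 = 80.0% | 0 |
| 75% | 11,500 / 150 = 76.7% | −3.3 points |
| 70% | 11,000 / 150 = 73.3% | −6.7 points |

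In every row three times as many patients were taught, and in no row did the assignment change anyone's score.

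**Illustration 2: a selection model (attendance rates and correlation assumed).** Suppose a patient attends when a latent normal score, correlated ρ with knowledge, exceeds a cut-off *c* set by the attendance rate *p*. Mean knowledge among attenders is then ρ φ(*c*) / *p* in SD units. Example with ρ = 0.3, 5% against 20%:

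- *p* = 0.05: φ(1.645) / 0.05 = 2.063
- *p* = 0.20: φ(0.842) / 0.20 = 1.400
- Difference: 0.3 × (1.400 − 2.063) = −0.199 SD

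The rates are assumptions. The 10% echoes the Background's upper figure for DSMES use. The 31% echoes the referral (not attendance) figure from the cited quality improvement study. The true effect of the intervention on knowledge is set to zero for the ρ columns. The last column instead assumes that the class raises knowledge by 0.5 SD in attenders of both arms, which gives an all-patient difference of 0.5 × (*p* intervention − *p* control).

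| Attendance, control vs intervention | ρ = 0 | ρ = 0.1 | ρ = 0.3 | ρ = 0.5 | All-patient difference |
|---|---|---|---|---|---|
| 5% vs 10% | 0 | −0.031 | −0.092 | −0.154 | +0.025 |
| 5% vs 20% | 0 | −0.066 | −0.199 | −0.331 | +0.075 |
| 10% vs 31% | 0 | −0.062 | −0.185 | −0.308 | +0.105 |

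The formula is linear in ρ, so a negative ρ gives the same sizes with the opposite sign. Under this model the attenders-only contrast shows none of the real all-patient gain when ρ = 0, and shows a difference that the intervention did not cause when ρ ≠ 0 and attendance differs.

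**The case against.** The strongest reply is that the plan never writes down the comparison being criticised. In Study Design the intervention-versus-control wording is attached to referrals, and the secondary outcomes follow in a separate sentence. That list also holds feasibility and acceptability, which Research Procedures (Objective 3) obtains from program staff and stakeholders with no control comparison, so being on the list does not by itself imply an arm contrast. Research Procedures uses intervention-versus-control wording for A1c but not for knowledge or satisfaction. This stands in part: it is fair to say that the use of the two measures is unspecified, and wrong to say that a particular invalid test is planned. But they are secondary outcomes of a cluster randomised trial, listed directly after the effect sentence and collected from clinics in both arms. A between-arm reading is the natural one, and nothing in the text rules it out.

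A reader might also infer that the plan promises a change in knowledge or satisfaction that it cannot deliver. No section promises a change score. Satisfaction with the class can only be asked of people who attended, so the absence of a pre-class or non-attender value is no defect there; it limits knowledge only. Nor can a pre-class knowledge item be excluded, because the attached data collection summary and the providers' survey form are not reproduced. Even with such an item, only attenders would have values.

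Finally, referral and attendance percentages are reported by clinic, so a tripling of attendance would be visible elsewhere in the results. That softens the false-null risk but does not remove the selection problem. The magnitudes above are indeed assumed.

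**Conclusion.** The concern holds as a matter of labelling and interpretation. On the visible text, knowledge and satisfaction exist only for attenders, after the class, and attendance is a post-randomisation result that the intervention aims to raise. A descriptive difference between arms can be calculated, but without further assumptions it is not an unbiased effect of the assigned intervention.

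The size depends on unknown attendance and selection. Under the assumed inputs it runs from zero (attendance equal in the arms, or unrelated to the score) to about 0.33 SD in the selection model, or 6.7 points in the simple example. The documents give no figures with which to narrow this.

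It would be going too far to conclude that the trial's effectiveness evidence as a whole is compromised. The primary referral comparison does not depend on these surveys, no test or decision rule rests on them, and the study is a pilot. The point should be corrected, but it does not threaten the main analysis.

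**What to change.** In the Objective 2 text of Study Design, Research Procedures, and Records, Privacy, and Confidentiality, state that patient satisfaction and diabetes knowledge are descriptive measures among DSMES attenders. Report them by clinic, alongside the numbers eligible, referred, attending and responding to the survey, and state that no between-arm effect of the intervention will be claimed from them.

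Optionally, if the providers' routine form already holds a pre-class knowledge score, ask the provider to supply the paired change summarised to the clinic level. It would still describe attenders only and would still carry no between-arm claim. This option is more than wording: the study team receives clinic-level aggregates without identifiers, so the provider would have to link the scores first.

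The main change needs no new data collection. Its cost is two fewer outcomes on which an intervention effect could be claimed.

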Studies examining barriers to DSMES have identified a variety of reasons for DSMES underutilization including barriers at the health system level, provider level and patient level. One of the fundamental barriers identified by the American Association of Diabetes Educators was lack of a DSMES referral from a provider. Referring a patient to DSMES necessitates clinician awareness and engagement, patient identification, a referral mechanism, and an available DSMES supplier, and barriers can and do occur throughout this process. The ongoing expansion of electronic health records (EHR) creates opportunities to more efficiently and comprehensively identify patients who could benefit from DSMES and supports electronic referral processes. A recent quality improvement study implemented an electronic DSMES referral process to identify and refer patients for DSMES at the four key time points recommended by the ADA, which, in combination with protocol training, increased DSMES referrals from 0% to 31%. The proposed study leverages unique statewide partnerships to implement and expand health information technology to automate patient identification and facilitate referrals to DSMES services. We hypothesize, however, that health information technology is necessary, but not sufficient, to drive DSMES utilization.

Availability of DSMES in Kentucky has increased but utilization remains low. As of 2019, there were 90 nationally recognized and accredited DSMES programs in Kentucky, which provided in-person classes in 80 of Kentucky's 120 counties. Healthy Living with Diabetes, an umbrella DSMES program administered by the Kentucky Department of Public Health (KDPH), is the largest DSMES program in the state. KDPH partners with 17 local health districts across Kentucky to provide free DSMES services in-person in 66 counties and via telehealth to residents in all 120 counties. The number of counties with DSMES services in Kentucky increased from 27 counties in 2012 to 80 counties in 2019. However, during this same period, annual DSMES participation decreased from a high of 14,545 participants in 2013 to 10,278 participants in 2019.

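### The plan gives no route for counting a referred patient who attends a non-KDPH programme, so attended/referred may be understated by an unknown amount that could differ by arm

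*Combined protocol and SAP*

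**What the plan says.** Research Procedures, Objective 2, lists the measure as "DSMES attendance (% attended/% referred at the clinic level". The referral count comes from the clinic health record and is not restricted by destination. On the source of attendance, the section says "DSMES attendance will also be reported by the clinics based on feedback data from the bidirectional referral system linking clinics with DSMES providers". For the period before the intervention it says "Clinics will also report number of DSMES referrals and DSMES attendance from the 9-month baseline period", without naming a source.

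Study Design, Objective 2, lists the "bidirectional e-referral system connecting clinics to the DSMES providers" among the components of the randomised intervention. It does not describe such a link for control clinics.

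The same Research Procedures paragraph then turns to other outcomes: "we will also be receiving data from the DSMES providers on patient satisfaction with the class and diabetes knowledge". It goes on: "KDPH will provide the study team with de-identified data for all patients from the two participating healthcare systems who attend DSMES". The Objectives section names KDPH as the DSMES partner and names no other. The Study Population text recruits KDPH providers for the interviews in Objectives 1 and 3.

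The Background describes a wider market. As of 2019 there were "90 nationally recognized and accredited DSMES programs in Kentucky, which provided in-person classes in 80" of the state's 120 counties. KDPH's umbrella programme is called the largest, not the only one. KDPH and its local partners "provide free DSMES services in-person in 66 counties and via telehealth to residents in all 120 counties".

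**The concern.** The denominator takes in every DSMES referral. The numerator depends on feedback from linked providers, and the only DSMES organisation visible in the plan is KDPH. A patient who is referred to another accredited programme and attends it enters the denominator but has no stated way into the numerator. The plan's own rule would then score that patient as not having attended.

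Three results depend on this. The attendance ratio would be too low. The A1c analysis of patients who attended DSMES would leave some attenders out of that subset. Any conclusion about DSMES utilization, the subject of the study hypothesis, would in practice concern KDPH only.

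The loss could also differ between arms. The feedback loop that supplies attendance is an intervention component. An electronic link to the partner's educators might also move intervention referrals to KDPH while control clinics keep their usual destinations. Moving a patient from one programme to another would then look like higher attendance, although no additional patient had been taught.

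**Working it through.** The plan states no attendance rate, KDPH share or referral destination, so there is no figure to reproduce. The check sets the counting rules side by side and then shows how the ratio behaves under declared assumptions.

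**1. Counting rules.** The plan writes the measure as one percentage over another; I read it as patients attended divided by patients referred.

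| Patient | In denominator? | Stated route to numerator? |
|---|---|---|
| Referred, attends KDPH | yes | yes, provider feedback |
| Referred, attends another programme | yes | none stated |
| Not referred, attends anywhere | no | outside the measure |

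Only the second row is misclassified.

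**2. What the Background figures can show.** If the 66 KDPH in-person counties lie within the 80 and the dates match, at least 80 − 66 = 14 counties (14/80 = 17.5%) had in-person classes only from other programmes. This shows that other programmes exist. It is not a loss rate, because KDPH telehealth reaches all 120 counties.

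**3. Referrals going outside KDPH.** Let p be true attendance among referred patients and w the share of referrals going outside KDPH. Assume that p is the same inside and outside KDPH and in both arms, and that no outside attendance is captured.

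- Observed attendance = p × (1 − w)
- Spurious difference, intervention minus control = p × (w control − w intervention)

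With p = 50% (assumed):

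| w control | w intervention | Observed control | Observed intervention | Difference |
|---|---|---|---|---|
| 20% | 20% | 0.5 × 0.8 = 40% | 0.5 × 0.8 = 40% | 0 |
| 20% | 10% | 0.5 × 0.8 = 40% | 0.5 × 0.9 = 45% | +5 points |
| 40% | 10% | 0.5 × 0.6 = 30% | 0.5 × 0.9 = 45% | +15 points |
| 10% | 20% | 0.5 × 0.9 = 45% | 0.5 × 0.8 = 40% | −5 points |

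With p from 20% to 60%, the second row gives +2 to +6 points (0.2 × 0.1 to 0.6 × 0.1) and the third +6 to +18 (0.2 × 0.3 to 0.6 × 0.3).

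**4. Feedback itself unequal.** If true attendance is 40% in both arms and the feedback captures 95% of it in intervention clinics and 80% in control clinics (both assumed), the observed rates are 0.4 × 0.95 = 38% and 0.4 × 0.80 = 32%, a spurious +6 points. With true attendance from 20% to 60%, the difference is +3 to +9 points.

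**5. Equal loss.** With 80% captured in both arms, a true 40% v 30% becomes 32% v 24%. The difference shrinks from 10 to 8 points, and the ratio stays at 1.33.

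Steps 3 and 4 are separate mechanisms. Using the same KDPH records in both arms would remove the second but not the first, because the first depends on where patients are sent.

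**The case against.** The strongest reply is that the plan never limits attendance to KDPH. The attendance sentence speaks of DSMES providers in general, and clinic staff extract the ratio from the health record, where a completion note from another programme could be found and counted. The sentence naming KDPH as supplier follows the text on satisfaction and knowledge surveys and may describe only that feed. It also covers both healthcare systems, hence both arms. Control clinics belong to the same organisations and are chosen to resemble the intervention sites. The Data Collection Summary, cited as the complete data list, is an attachment not reproduced in the text and may settle the matter. Attendance is also a secondary outcome in a pilot.

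Much of this stands, and it rules out four stronger readings that a reader might infer:

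- That attendance is observed only for KDPH. This is an inference; the text merely gives no other explicit route.
- That all DSMES taken elsewhere counts as non-attendance. Attendance without a referral is outside the ratio.
- That 17.5% of attendance is lost. Telehealth coverage defeats this, and the documents do not say how many of the 90 programmes serve the study clinics or sit under the KDPH umbrella.
- That the bias is known to favour the intervention. A shift of referrals to KDPH is plausible, but no destination is documented for either arm.

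The gap itself survives. No rule says that outside completion notes are to be sought or counted. No source of feedback is described for control clinics. The Data and Safety Monitoring Plan describes validation of record reporting for intervention clinics only.

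**Conclusion.** The concern holds as a gap in how a secondary outcome is measured. As written, a referred patient who attends a non-KDPH programme has no stated route to the numerator, so attended/referred is understated wherever such patients exist, and the A1c subset of attenders is misclassified with them. The loss could differ by arm, through referral destination or through a feedback source that is part of the intervention. If control clinics lost more, the error would favour the intervention.

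Neither size nor direction can be derived from the documents. The illustrations (0, +5 and +15 points at an assumed 50% attendance, and −5 if the shares are reversed) rest on assumed shares and on no outside attendance being captured. The primary outcome, referrals, is unaffected. The point deserves correction before attendance or utilization is reported. It could be closed if the unseen Data Collection Summary already specifies a common source and a rule for other programmes.

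**What to change.** - Take attendance from the same source for all 11 clinics (4 intervention, 7 control), and name that source for the baseline period.
- Add referral destination to the clinic report as KDPH, other or unknown, including baseline where it was recorded. Report the non-KDPH share by arm.
- Keep attended over all referred as the planned measure. Show attended over KDPH-referred beside it as a matched sensitivity measure, noting that destination arises after randomisation. It should not replace the planned denominator, because the intervention may change who is referred to KDPH.
- Count non-KDPH completion documented in the health record by one rule in both arms, and use the same rule to define the A1c subset.
- Word attendance and utilization conclusions as KDPH DSMES unless attendance elsewhere is captured.

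**Cost.** One further field in an aggregate report, plus changes of wording. The claim becomes narrower, and some destinations will be unknown. Data reach the team already aggregated, and the change log shows that the item on new enrolment or data collection was switched to no in December 2024. The clinics may therefore have to extract again. If that is not feasible, the wording and a statement of the limitation can still be corrected before reporting.
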